### 3.4 Statistical Interim analyses and stopping guidance

One interim analysis was performed when 70% of the expected information will be available (112 patients with complete follow-up). The critical p-value was set at 0.01.

### 3.5 Timing of final analysis

The trial is scheduled to end with the final 12-month follow-up visit (expected around the end of June 2023). The data will be cleaned, verified, and locked. The final analysis will begin once the final gel has been confirmed by the Principal Investigator.

# **Section 4: Statistical Principles**

# 4.1 Confidence Intervals and P-values

The interim analysis was performed when about 70% of the expected information is available (112 patients with complete follow-up), with a significance boundary p-value of 0.01. Consequently, the final analysis will have to be performed with a significance boundary **p-value of 0.043**.

All other tests will be two-sided, with p values of 0.05 or less denoting statistical significance. 95% confidence interval will be used to report effect estimates of secondary endpoints.

# 4.2 Adherence and protocol deviations

Treatment compliance for each patient will be calculated as the number of days that study drug was actually taken (i.e., number of days on treatment minus days of temporary discontinuation) divided by the number of days of follow-up. The percentage of patients at least 75% compliant will also be reported (as proposed by Israelsen M, et al. Lancet Gastroenterol Hepatol 2023;8:604).

Study drug discontinuation is defined as a minimum of 14 consecutive days without study drug intake.

# 4.3 Analysis populations

### Modified intention to treat population (mITT)

This population will include all randomized patients who received at least 1 dose of the study drug. All patients will be analyzed in the arm defined by the random allocation. Patients wrongly included (ineligible patients that were erroneously randomized) will be excluded from the analysis.

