### **3.2 Randomization**

All consecutive severe cirrhotic patients with large ascites who will be admitted to the participating centers will be screened for eligibility (see inclusion and exclusion criteria). After the patient signs the informed consent form, and after eligibility is documented based on inclusion / exclusion criteria mentioned above, the Investigator will connect to the CleanWeb web site (chrub.tentelemed.com/). For each new patient, the investigator will use the eCRF to include the patient into the study and the Interactive Web Response System

(IWRS) will affect a randomization arm to the patient. The IWRS center (INSERM CIC 1431, Besancon, France) will allocate treatment based on a pre-specified randomization list, generated by the data manager ([name]) of the study, using study center as a stratification parameter. A list of treatment kit numbers corresponding to each treatment arm will be centrally generated by LC2 Pharma Company ([name]. Contact: [name]) and the treatment kits will be prepared in accordance with this list. Numbers will not be reused regardless of the status of the use of the corresponding study drug. The randomization will be performed in a 1:1 ratio, the number of subjects per block, block sequences will only be known by the methodologist (Pr [name] and [name]) and the data manager of the study. The IWRS (INSERM CIC 1431, Besancon, France) randomizes the patient into one of the two study arms and affects a randomization number as well as a treatment kit number to the patient. The IWRS developed by INSERM CIC 1431 ensures that the randomization is confirmed by email to the investigator and to the sponsor. The IWRS enables the randomization of patients at any time of the day throughout the whole study period. A technical helpdesk will provide support to investigators by phone or email. A web demonstration will be carried out in each participating center. In addition, an instruction manual describing the randomization process performed by the IWRS will be provided by the Clinical Research Assistant of the sponsor of the study to each participating center.

All patients randomized by the IWRS are irrevocably enrolled in the study, whether or not they are subsequently found to be eligible or actually receive the allocated treatment. As a consequence, patients should be followed until their last visit, until stopping rules apply or death.

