### Per protocol population

This population will exclude from the analysis:

- patients treated with the to the wrong study drug according to the arm defined by the random allocation, if applicable.

- patients who did not reach 75% compliance as defined in 4.2.
- patients who discontinued the study drug for more than 14 consecutive days

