#### **Exclusion criteria**

- Pregnant or breastfeeding woman
- Vulnerable person under French law
- Individual under legal protection measure
- Individual unable to express their consent
- Person under 18 years of age and over 80 years of age
- Transplanted patients, HIV infection (or patients who deny HIV serology) or immunosuppressive therapy (including patients under corticosteroids for severe alcoholic hepatitis if the patients respond to steroids with improvement of liver function)
- Patients with a liver transplant project and an estimated waiting time for liver transplantation of 3 months or less
- History of SBP
- Any present bacterial infection
- Patient who have received a TIPS procedure before the randomization
- Patients with an alfapump® system (added in protocol V5)
- Patient receiving antibiotics (including rifaximin) in the 7 days preceding the inclusion in this study except for patients participating to the microbiota study (15 days).
- Hypersensitivity to rifaximin, derivatives of rifamycin or one of the constituents of the preparation
- Hepatocellular carcinoma outside the Milan criteria, other cancer at a palliative stage
- Any clinical situation with a very low short-term prognosis (other than cirrhosis), i.e. a survival estimated lower than one month (added in protocol V5)
- Gastrointestinal bleeding within 7 days
- Intestinal obstruction
- Grade 3 hepatic encephalopathy (HE) during the previous 6 months before randomization
- Chronic heart failure (stage III or IV of the New York Heart Association [NYHA] Functional Classification)
- Patient judged as noncompliant
- Patients who cannot receive a clear information and who have no trusted relatives
- Patient who refuses the participation agreement by signing the information form and consent as defined in the protocol.
- Exclusion period from another biomedical study

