### 5.2 Withdrawal/Follow-up

Criteria for stopping the study are:

• withdrawal of consent,

- liver transplantation,
- loss to follow up
- enrollment of ineligible subjects.

Patients withdrawn from the study for withdrawal of consent, liver transplantation or loss to follow up will be censored at the date of withdrawal. Ineligible subjects will be excluded from the mITT analyses.

For all other patients, monitoring of the patient will continue, follow-up will focus on collecting the endpoints of the trial:

- vital status,
- date of death,
- complications of liver cirrhosis (HE, gastrointestinal bleeding and HRS),
- dates and length of hospital stays during the 12 months following inclusion in the trial

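### Treated patients later ruled ineligible are deleted from the mITT and may lose their 12-month vital status, and no listed efficacy analysis expressly keeps them

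*SAP*

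**What the plan says.** **Enrolment (SAP 3.2).** "All patients randomized by the IWRS are irrevocably enrolled in the study, whether or not they are subsequently found to be eligible". The section adds that, as a consequence, "patients should be followed until their last visit, until stopping rules apply or death".

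**Analysis set (SAP 4.3, mITT).** The set takes randomised patients with at least one dose, in the arm allocated. Then: "Patients wrongly included (ineligible patients that were erroneously randomized) will be excluded from the analysis".

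**Stopping and follow-up (SAP 5.2).** Four reasons for stopping the study are listed: consent withdrawal, liver transplantation, loss to follow-up, and enrolment of an ineligible patient. The first three are handled in one way: "Patients withdrawn from the study for withdrawal of consent, liver transplantation or loss to follow up will be censored at the date of withdrawal". The fourth is handled in another: "Ineligible subjects will be excluded from the mITT analyses". The section then turns to everyone else: "For all other patients, monitoring of the patient will continue, follow-up will focus on collecting the endpoints of the trial". Vital status and date of death head the list of what is collected for them.

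**Other analyses.** The only sensitivity analysis of the primary endpoint in 6.2 removes further patients, those with suspected alcoholic hepatitis and a high Maddrey score. The safety population in 4.3 keeps every exposed patient, but 6.4 uses it for harms.

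**The concern.** The primary endpoint is death from any cause within 12 months, in 160 patients. A patient who was randomised, treated and died can be taken out of that comparison by a later ruling on eligibility. Three things make this worth settling before the database is locked.

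- The SAP treats ineligibility in two ways that do not sit well together. It is irrelevant to enrolment in 3.2, and a reason to stop and be removed in 5.2.
- Patients stopped for the other three reasons are censored and contribute their time at risk. Only the ineligible contribute nothing.
- If endpoint collection ends for these patients, their 12-month status may be unknown, and the effect of removing them could not be examined afterwards. Safety reporting may still pick up some deaths, since 6.4 runs to the study end date, but it is not an efficacy analysis.

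At stake is whether the trial can show that its mortality result does not depend on who was ruled ineligible.

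**Working it through.** **Step 1. The text side by side.**

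| Question | 3.2 | 4.3 | 5.2 |
|---|---|---|---|
| Does ineligibility undo enrolment? | No, enrolment is irrevocable | Not addressed | It is a reason for stopping the study |
| Are treated ineligible patients in the mITT? | Not addressed | No | No |
| Are they followed for endpoints? | Yes, unless a stopping rule applies | Not addressed | Continued only for patients outside the stopping list |

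The second row shows no contradiction: 4.3 and 5.2 give the same answer, and 3.2 defines no analysis set. The first row is the tension. The third row is unclear. The stopping-rule clause in 3.2 can be read as giving way to 5.2, and on that reading vital status need not be collected.

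**Step 2. Limits on the ruling.** The description of these patients in 4.3 as randomised in error points to their status at randomisation. The SAP does not say that only pre-randomisation data may be used, that the ruling is blind to arm and outcome, or that it is made before lock.

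**Step 3. Size.** The SAP gives no figure on this point to reproduce and no count of ineligible patients. I assume 2, 4 or 8 of 160 (1.25%, 2.5%, 5%).

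Inputs from SAP 3.3: 80 per arm, 60% 12-month mortality (the placebo projection, applied to both arms as the null), 10% dropout, final boundary p < 0.043. My assumptions: exponential survival and dropout, an unstratified log-rank test, and the final test alone without the interim look.

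Check on the model:
- 12-month cumulative hazards: death −ln(0.4) = 0.916; dropout −ln(0.9) = 0.105.
- Probability of an observed death: 0.916/(0.916 + 0.105) × (1 − 0.4 × 0.9) = 0.897 × 0.64 = 0.574.
- Expected deaths: 160 × 0.574 = 91.8, which is also the simulated mean.

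Two-sided error, 40,000 trials per setting, simulation standard error about 0.001:

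| Who is excluded | 2 | 4 | 8 |
|---|---|---|---|
| Nobody | 0.0431 | 0.0431 | 0.0431 |
| Random patients | 0.0435 | 0.0428 | 0.0435 |
| Deaths, regardless of arm | 0.0429 | 0.0435 | 0.0432 |
| Rifaximin patients, regardless of outcome | 0.0432 | 0.0427 | 0.0428 |
| Deaths, three quarters from rifaximin | – | 0.0469 | 0.0548 |
| Deaths, all from rifaximin | 0.0462 | 0.0520 | 0.0804 |

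The first four rows are flat. Error rises only when exclusion depends on arm and outcome together. The last row is a bound. To reach 0.0804, 8 of about 91.8/2 = 45.9 rifaximin deaths (17%) would have to be ruled ineligible, and no placebo death.

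**The case against.** **Enrolment is not analysis.** Section 3.2 governs the randomisation system and follow-up, and allows follow-up to end when a stopping rule applies; 5.2 lists the rules. A reader might infer that the SAP contradicts itself on who is analysed. It does not, since 4.3 and 5.2 agree. What stands is narrower: irrevocable enrolment regardless of eligibility sits badly with ineligibility as a stopping reason, and the follow-up of these patients is left open.

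**Excluding ineligible patients can be legitimate.** It can, when it rests on facts fixed before randomisation and is judged blind. The wording of 4.3 leans that way, the trial is double-blind (3.1), and data are cleaned and locked before the final analysis (3.5). The procedure may also be in the protocol, which is not at hand. So the fair statement is that the SAP neither sets these limits nor cites a place that does.

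**A reader might infer that the exclusion inflates the type I error.** The documents do not support that. Inflation needs selection by both arm and outcome, and a double-blind trial offers no evident mechanism for it. The larger figures also rest on assumed counts.

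**A reader might also infer that early deaths could be reclassified as ineligible** through the exclusion criterion on one-month survival. That criterion in 5.1 is confined to situations other than cirrhosis and concerns prognosis at entry, so it does not carry that argument.

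**Late change.** Sections 3.4 and 4.1 describe the interim analysis as performed. That is a reason to leave the primary set alone, not a reason against adding a sensitivity analysis.

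**Conclusion.** The point holds as a cheap improvement. The SAP enrols patients irrevocably in 3.2, makes ineligibility a reason for stopping in 5.2, and deletes treated ineligible patients from the mITT in 4.3 and 5.2. It leaves their 12-month vital status uncertain and lists no efficacy analysis that expressly keeps them. It does not state the limits that would make the exclusion safe.

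The size is unknown because no count is given. On the assumed 2, 4 or 8 of 160 and the model above, exclusion that does not depend on both arm and outcome leaves the error near 4.3-4.4%. Bias should be checked for, not presumed. Nor do the documents show that vital status will in fact be lost; they only fail to secure it. The finding concerns the SAP as written and would shrink if the protocol already sets the rule.

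**What to change.** 1. **Reconcile 3.2, 4.3 and 5.2.** Say plainly what a later finding of ineligibility changes. Ascertain 12-month vital status for randomised patients found ineligible, subject to consent and as far as it is available.
2. **In 6.2, add one sensitivity analysis** of 12-month mortality in all randomised patients as allocated, including those found ineligible.
3. **In 4.3, keep the primary mITT as defined**, but limit the exclusion to failures of entry criteria judged on pre-randomisation data, blind to arm and outcome, before database lock. Tabulate the excluded patients by arm with reasons. If the protocol already sets this rule, cite it.

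The cost is some SAP wording, one extra analysis and a few vital-status checks. Some of these may be retrospective, since 3.5 expects the last 12-month visits around the end of June 2023. The definition of the primary set does not change, so this route avoids redefining it after the interim analysis. The revision should be dated as made after that analysis.

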### Per protocol population

This population will exclude from the analysis:

- patients treated with the to the wrong study drug according to the arm defined by the random allocation, if applicable.

- patients who did not reach 75% compliance as defined in 4.2.
- patients who discontinued the study drug for more than 14 consecutive days

### Safety population

For each study drug, the safety population will include all patients exposed to at least one dose of said study drug.

# **Section 5: Trial Population**

# 5.1 Eligibility

Provide a list of eligibility criteria. Note if any changes to the eligibility criteria occurred at any time during the study (e.g., after randomization of the 1st patient).

### Inclusion criteria

- Man or woman aged  $\geq 18$  and  $\leq 80$  years
- Cirrhosis diagnosed on clinical, radiological and/or histological findings
- Patients with large ascites (i.e., grade 3 ascites requiring paracentesis). Patients with grade 2 ascites are also authorized.
- Ascites with a low protein level in ascitic fluid (< 15 g/L) with one of the following three conditions:1) impaired renal function defined by serum creatinine  $\geq$  106 µmol/L, uremia  $\geq$  9 mmol/L or serum sodium

 $\leq$  130 mmol/L), or 2) severe liver impairment defined by Child-Pugh C or Child-Pugh B  $\geq$  9 with serum total bilirubin levels  $\geq$  51 µmol/L.

- Patient who signed an informed consent form
- Patient with a social security system
- Woman must be surgically sterile or be postmenopausal, or must agree to use effective contraception during the study if childbearing potential
- Patients who need a TIPS if the procedure is performed 3 months or more following the randomization
- Patients with severe alcoholic hepatitis can be considered for inclusion if the MELD score < 30 and the Maddrey Discriminant Function < 60 providing that the patient is not infected (and consequently, will not receive antibiotics) and has not yet received corticosteroid (if necessary). Patients not responding to corticosteroid at day 7 (according to the Lille score) could be include after a wash-out of steroids for a period of 7 days.

#### **Exclusion criteria**

- Pregnant or breastfeeding woman
- Vulnerable person under French law
- Individual under legal protection measure
- Individual unable to express their consent
- Person under 18 years of age and over 80 years of age
- Transplanted patients, HIV infection (or patients who deny HIV serology) or immunosuppressive therapy (including patients under corticosteroids for severe alcoholic hepatitis if the patients respond to steroids with improvement of liver function)
- Patients with a liver transplant project and an estimated waiting time for liver transplantation of 3 months or less
- History of SBP
- Any present bacterial infection
- Patient who have received a TIPS procedure before the randomization
- Patients with an alfapump® system (added in protocol V5)
- Patient receiving antibiotics (including rifaximin) in the 7 days preceding the inclusion in this study except for patients participating to the microbiota study (15 days).
- Hypersensitivity to rifaximin, derivatives of rifamycin or one of the constituents of the preparation
- Hepatocellular carcinoma outside the Milan criteria, other cancer at a palliative stage
- Any clinical situation with a very low short-term prognosis (other than cirrhosis), i.e. a survival estimated lower than one month (added in protocol V5)
- Gastrointestinal bleeding within 7 days
- Intestinal obstruction
- Grade 3 hepatic encephalopathy (HE) during the previous 6 months before randomization
- Chronic heart failure (stage III or IV of the New York Heart Association [NYHA] Functional Classification)
- Patient judged as noncompliant
- Patients who cannot receive a clear information and who have no trusted relatives
- Patient who refuses the participation agreement by signing the information form and consent as defined in the protocol.
- Exclusion period from another biomedical study

### 5.2 Withdrawal/Follow-up

Criteria for stopping the study are:

• withdrawal of consent,

- liver transplantation,
- loss to follow up
- enrollment of ineligible subjects.

Patients withdrawn from the study for withdrawal of consent, liver transplantation or loss to follow up will be censored at the date of withdrawal. Ineligible subjects will be excluded from the mITT analyses.

For all other patients, monitoring of the patient will continue, follow-up will focus on collecting the endpoints of the trial:

- vital status,
- date of death,
- complications of liver cirrhosis (HE, gastrointestinal bleeding and HRS),
- dates and length of hospital stays during the 12 months following inclusion in the trial

# **5.3 Baseline Patient Characteristics**

The description and initial comparison of randomized groups will focus on the demographic characteristics, clinical features of liver disease, previous complications of cirrhosis, and pre-existing treatment. Past medical history, concomitant treatments and biological results will also be compared.

Quantitative variables will be in the form of a table showing the number of values and the number of missing data, the mean and median, standard deviation, coefficient of variation, the minimum and maximum for each group and for the overall population.

Categorical variables will be in the form of a table revealing the number of values and the number of missing data, the percentage of each category and the confidence intervals for each group and for the overall population.

Continuous variables will be compared using Student's t-test or the Mann-Whitney test, as appropriate. Categorical variables will be compared using the Chi-squared test or Fisher's exact test, as appropriate.

The description will include the following variables:

Age, years Sex Weight, kg BMI, kg/m^2

Comorbidities

- Type 2 diabetes
- Hypertension
- Severe acute alcoholic hepatitis (Maddrey score  $\geq$  32)
- Hepatocellular carcinoma within Milan criteria
- Alcohol consumption
- Daily alcohol consumption if not abstinent, g

Cause of liver cirrhosis

- Alcohol
- Hepatitis B / B Delta
- Hepatitis C
- MAFLD (=NASH)
- Other

Child Pugh score

MELD score

Liver parameters

- Alanine aminotransferase, UI/L
- Aspartate aminotransferase, UI/L
- Gamma glutamyl transferase, UI/L

- Alkaline phosphatase, UI/L
- Bilirubin, µmol/L
- Platelet count, G/L
- International normalized ratio
- Prothrombin index
- Albumin, g/L
- Creatinine, µmol/L
- Baseline CRP
- CRP Day 30
- Difference between baseline and Day 30 CRP

# **Section 6: Analysis**

# **6.1 Outcome Definition**

### Primary endpoint

12-month survival. Death, whatever the recorded cause, will be considered as the primary endpoints. The date and, whenever possible, the causes of death will be recorded.

### Secondary endpoints

- Hospital survival and, 3- and 6-month survival
- Incidence of SBP during follow-up with date of diagnosis
- Incidence of the other complications of liver cirrhosis during follow-up (HE, gastrointestinal bleeding and HRS) with dates of diagnosis
- Number of days that patients spend in hospital during follow-up
- Safety analysis of the study drug
- The quantitative variations of IL-6, LPS, copeptin, CRP, vWF antigen in serum between day 1 and day 30
- The composition of the intestinal microbiota (quantity and quality of main bacterial strains) in 25 patients from groups A and B at day 1, and at months 3, 6, 12 and 18.

### **Definitions:**

**Spontaneous bacterial peritonitis**: Diagnosis of SBP is based on the neutrophils cell count in ascitic fluid (> 250/mm^3) regardless the result of the ascitic fluid culture.

**Hepatic encephalopathy** (HE): HE is a brain dysfunction caused by liver insufficiency and portosystemic shunting. HE produces a wide spectrum of nonspecific neurological and psychiatric manifestations. Clinical HE is grading according to the West-Haven criteria.

**Hepatorenal syndrome** (HRS) is essentially a diagnosis of exclusion (i.e., there is an absence of other identifiable causes of renal failure). The hepatorenal syndrome is characterized by the following features in a patient who has established or clinically evident chronic liver disease:

- i. Serum creatinine > 133  $\mu$ M (15 mg/L),
- ii. Absence of hypovolemia as defined by no sustained improvement of renal function (creatinine decreasing to <133µmol/L) following at least 2 days of diuretic withdrawal (if on diuretics), and volume expansion with albumin at 1g/kg/day up to a maximum of 100g/day.
- iii. Absence of shock,
- iv. No current or recent treatment with nephrotoxic drugs,
- v. Absence of parenchymal renal disease as defined by proteinuria <0.5 g/day, no microhaematuria (<50 red cells/high powered field), and normal renal ultrasonography

